9.4 Permanent Discontinuation in Response to Adverse Events

Grade 1 or 2

In general, a participant who develops a Grade 1 or 2 AE as defined by the DAIDS Table for Grading Adult and Pediatric Adverse Events, Version 2.1 dated July 2017 regardless of relationship to study medication may continue study medication use.

Grade 3

For participants who develop a Grade 3 AE as defined by the DAIDS Table for Version 2.1 dated July 2017 that is judged by the study investigators to be unrelated to study medication, the study medication may continue. The study medication must

be permanently discontinued for participants who develop a Grade 3 AE judged by a site PI/designee to be related to the study medication.

Grade 4

If a participant develops a Grade 4 AE as defined by the current DAIDS Table for Grading Adult and Pediatric Adverse Events and the AE is determined to be related to study medication, then study medication must be permanently discontinued.

9.5 HIV-1 Infection

If HIV seroconversion occurs during the time of study medication use, the study medication may continue.

9.6 Criteria for Early Termination of Study Participation

Participants may voluntarily withdraw from the study for any reason at any time. The study investigators also may withdraw participants from the study to protect their safety and/or if they are unwilling or unable to comply with required study procedures (see section 9.3 for further details). Participants also may be withdrawn if Gilead Sciences, government or regulatory authorities, including the FDA, Health Canada, PSRT or site IRBs/REBs or the Protocol Chair terminate the study prior to its planned end date. Detailed reasons for the withdrawal of a participant will be documented in the research record. Every reasonable effort will be made to continue to follow the participant as scheduled for safety.

10 STATISTICAL CONSIDERATIONS

10.1 Overview and Summary of Design

This is a Phase 4, single-arm, open label cohort study of treatment for chronic HCV infection during pregnancy in approximately 100 HCV-infected pregnant women receiving a 12-week (84 day) course of SOF/VEL and their infants. Maternal participants will be considered evaluable if they have a HCV viral load result at the Post-Treatment visit (V6) or have a HCV viral load drawn from clinical care that occurs during or any time after the V6 visit window. Pregnancy and neonatal outcomes will be compared to a historical cohort of pregnant women with active HCV from each of the participating study sites.

10.2 Study Endpoints

Pregnant women meeting all of the eligibility criteria in sections 5.2 and 5.3 will be enrolled into the study and followed prospectively through approximately 12 weeks after the last dose of study medication. Infants will be enrolled upon delivery and followed prospectively through approximately one year of age. Maternal and infant study endpoints are described in detail in Section 3.

10.3 Sample Size

The sample size of approximately 100 participants was chosen in order to determine if a clinically meaningful difference exists between the prospective treatment cohort and the historical or published comparison groups regarding preterm birth <37+0 weeks' gestation and maternal SVR12.

To estimate the sample size required for maternal SVR12, a baseline SVR12 of 97% was used. This estimate was based on a 30% prevalence of HCV genotype 3 among young persons and the published rate of SVR12 for all genotypes³³. For maternal SVR, using an exact binomial test with a nominal 10% one-sided significance level will have 82% power to detect the difference between the Null hypothesis proportion, π_0 of 97% (published rate of SVR12 with SOF/VEL) and the Alternative proportion, π_1 , of 92% when the sample size is 100.

For the primary neonatal outcome of preterm birth <37+0 weeks' gestation, using Fisher's exact test a sample size of 100 will identify a difference of 13 percentage points in preterm birth rates (80% power 2-sided alpha = .05). The published preterm birth rate of 23% among HCV+ pregnant women at the University of Pittsburgh was used to calculate this estimate³⁴.

10.4 Data Collection and Analysis

10.4.1 Study Data Collection

All study data will be entered into the REDCap electronic data capture system maintained by the University of Pittsburgh.

10.4.2 Analysis of Maternal Safety

Pregnancy and delivery outcomes will be compared to a historical control group of pregnant women with active HCV (defined as a detectable HCV RNA) that delivered at the same hospitals where the study participants are enrolled. This retrospective cohort data will be collected using a separate protocol. Differences in frequency of each outcome will be determined by Fisher's exact test. Further, an adjusted analysis based on the collected maternal factors will be conducted in order to determine if any of the findings were related to treatment with SOF/VEL or due to a confounder using regression methods. In addition, all adverse events will be reported descriptively, noting relationship to the study medication as well as any grade 3 or 4 adverse events.

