5 STUDY POPULATION

5.1 Selection of the Study Population

5.1.1 Recruitment and Retention

Recruitment will take place at multiple study sites and according to the site's recruitment SOP. All recruitment materials and procedures will be approved prior to use by the site/local IRB/REB.

The importance of retention will be stressed to the participant at each visit as part of protocol adherence counseling and as per the site's retention SOP. Once a participant is enrolled, the study staff will make every effort to retain the participant in follow-up. If a participant is lost to follow-up or is discontinued from the study prior to the completion of the final maternal visit evaluating SVR12, then an additional/replacement participant will be enrolled into the study from any participating site.

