10.4.3 Analysis of Neonatal Safety

Neonatal outcomes will be compared to a historical control group of infants who had perinatal HCV exposure. Differences in frequency of each outcome will be

determined by Fisher's exact test. Further, an adjusted analysis based on the collected maternal factors will be conducted in order to determine if any of the findings were related to treatment with SOF/VEL or due to a confounder using regression methods. In addition, all adverse events will be reported descriptively, noting relationship to the study medication as well as any adverse events grade 3 or 4.

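### The preterm-birth and NICU comparisons with historical controls take no account of site: the Fisher test is unstratified and the planned adjustment does not name site

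*Protocol*

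**What the plan says.** Section 10.1 describes a multi-site single-arm cohort of about 100 women and sets the comparator: "Pregnancy and neonatal outcomes will be compared to a historical cohort of pregnant women with active HCV from each of the participating study sites". Section 10.4.2 restricts the maternal controls to women "that delivered at the same hospitals where the study participants are enrolled" and says that their data are gathered under a separate protocol. Section 10.4.3 says: "Neonatal outcomes will be compared to a historical control group of infants who had perinatal HCV exposure".

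Both sections fix the same test: "Differences in frequency of each outcome will be determined by Fisher's exact test". Section 10.3 also names Fisher's exact test for preterm birth, the second primary endpoint. Both analysis sections go on to say that "an adjusted analysis based on the collected maternal factors will be conducted", using regression, so as to separate a treatment effect from confounding. The factors are not listed and site is not mentioned.

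On recruitment, section 5.1.1 states no site quota and says that when a woman is lost before the SVR12 visit, "an additional/replacement participant will be enrolled into the study from any participating site". The only preterm rate given is 23%, from one institution (section 10.3).

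**The concern.** Drawing controls from the same hospitals holds local practice constant only if the comparison is made within hospitals, or if each hospital has the same share of both cohorts. A single pooled 2x2 table does neither. If the treated cohort leans towards a hospital with a high preterm rate and the controls do not, the pooled table shows an excess with no drug effect. If the lean is the other way, it shows a benefit.

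The outcomes at stake depend partly on local practice. Section 3.2 counts iatrogenic as well as spontaneous preterm delivery, and section 3.4 lists NICU admission among the neonatal outcomes. With no randomised comparator, the historical comparison is the only basis for a statement about preterm birth. Site is a likely confounder that can be measured, so leaving it out of both stated analyses is an avoidable weakness.

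**Working it through.** **The plan's own figure.** Section 10.3 claims 80% power to identify a 13-point difference in preterm birth from 23%, with a sample size of 100 and two-sided alpha 0.05. Exact Fisher power for 23% against 10% with 100 treated women is 64.8% with 100 controls, 75.6% with 150, about 80% with 200 and 84.7% with 300. The claim is thus met with about 200 controls, a number the protocol does not state. The checks below therefore use 100 to 300 controls.

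**Inputs.**
- From the protocol: 100 treated women, two-sided 5% Fisher test, preterm rate 23% at one site (call it A).
- Assumed, because the protocol gives no figure: a preterm rate r of 12% or 15% at all other sites, site A's share of each cohort, and the number of controls.
- No drug effect.

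**Spurious difference.** The crude rate in a cohort is s x 0.23 + (1 - s) x r, where s is site A's share. The spurious difference is therefore (s treated - s control) x (0.23 - r).

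| Share of A, treated vs control | r | Crude rates | Spurious difference |
|---|---|---|---|
| 70% vs 30% | 12% | 19.7% vs 15.3% | 0.40 x 0.11 = 4.4 points |
| 70% vs 30% | 15% | 20.6% vs 17.4% | 0.40 x 0.08 = 3.2 points |
| 70% vs 50% | 12% | 19.7% vs 17.5% | 0.20 x 0.11 = 2.2 points |
| 70% vs 50% | 15% | 20.6% vs 19.0% | 0.20 x 0.08 = 1.6 points |

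Reversing the shares reverses the sign.

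**False-positive rate of the pooled Fisher test** (exact enumeration over both cohorts, nominal 5%):
- Equal site mixes: 3-4%.
- 70% vs 50%: about 4-7% across 100 to 300 controls.
- 70% vs 30%: about 6-9% with 100 controls and 9-14% with 200, rising to at most 16% with 300.

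**Masking.** Take a true effect equivalent to 23% falling to 10%, applied as a constant odds ratio of (0.10/0.90)/(0.23/0.77) = 0.37, with r = 12% and 200 controls. Fisher power is 67% when both cohorts are split 50/50. It is 35% when site A holds 70% of the treated women and 30% of the controls.

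**Does stratifying help?** In a simulation of 20,000 runs with a wider assumed gap (15% and 30%), 200 controls, and the high-rate group supplying 70% of treated women but 30% of controls, pooled Fisher rejected 20% of the time under no effect. A site-stratified Cochran-Mantel-Haenszel (CMH) test rejected about 5%. With a true effect of the size above, Fisher power was 39% and CMH power 76%, against 77% for Fisher with balanced shares. An exact CMH test would tend to reject somewhat less often than these figures.

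**The case against.** Several stronger readings are tempting, and the protocol does not support them.

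- **That the Fisher test alone decides attribution.** The next sentence of 10.4.2, repeated in 10.4.3, commits to a regression whose stated purpose is to separate treatment from confounding. Fisher is the crude comparison.
- **That the regression excludes site.** The factors are not listed, so the accurate statement is that site is not named. A covariate list can properly sit in a statistical analysis plan, which is not available here.
- **That controls arrive in proportion to each hospital's past HCV deliveries, so the two mixes must differ.** The protocol says nothing of the kind. Control sampling is governed by another protocol, which may match or set quotas by site. If recruitment and control accrual both follow hospital volume, the mixes may be close.
- **That the bias is large.** Every site rate and share beyond the 23% is assumed. The spurious 1.6-4.4 points is well below the 13 points the trial is sized on, and the milder imbalance leaves the test near its nominal level.

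It is also fair to say that same-hospital controls already remove differences in setting, leaving only unequal shares. For very rare outcomes such as maternal or neonatal death, a stratified test would add little.

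These points limit the size of the concern but do not remove it. The choice of test is not left to a later document: sections 10.3, 10.4.2 and 10.4.3 fix it, and an analysis plan that follows them inherits a comparison without stratification.

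**Conclusion.** The concern holds in a limited form. The stated primary comparison for preterm birth, and those for the delivery and neonatal outcomes, pool all sites. The planned adjustment does not name site, and nothing shown keeps the two site mixes alike. Whether bias will occur cannot be told from the protocol. Under the assumed rates it is small for a moderate imbalance and becomes material only for a strong one, such as 70% against 30%, where the false-positive rate roughly doubles or triples relative to equal mixes and a real reduction could be masked. This is a worthwhile improvement in specification. It does not show that the comparison is invalid.

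**What to change.** In sections 10.4.2 and 10.4.3:

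1. Name site as a covariate in the adjusted regression, with very small sites combined by a rule fixed before the outcomes are examined.
2. For preterm birth and other common outcomes such as NICU admission, report a site-stratified exact CMH comparison as the basis for inference.
3. Keep the pooled Fisher test as the crude comparison, and as the test for very rare outcomes.
4. State how site is assigned, for example enrolling site for treated women and delivery hospital for controls, since section 7.4.3 allows treated women to deliver elsewhere.

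If the separate control protocol already ties control shares to enrolment by site, a sentence saying so would answer most of the concern.

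The cost is a change of wording. No new participants are needed, and site should already be recorded because controls are defined by hospital. The downside is a slight loss of information from very small sites.

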10.4.3 Analysis of Neonatal Safety

Neonatal outcomes will be compared to a historical control group of infants who had perinatal HCV exposure. Differences in frequency of each outcome will be

determined by Fisher's exact test. Further, an adjusted analysis based on the collected maternal factors will be conducted in order to determine if any of the findings were related to treatment with SOF/VEL or due to a confounder using regression methods. In addition, all adverse events will be reported descriptively, noting relationship to the study medication as well as any adverse events grade 3 or 4.

10.4.4 Analysis of HCV Endpoints

The maternal SVR12 rate in the study will be compared to the historical SVR12 rate published in the literature of 97% for non-cirrhotic patients with an approximately 30% prevalence of genotype 3 infection³³ using a one-sided exact binomial test. The reported rate of perinatal transmission in HCV mono-infection is between 4-7% as noted in a large metanalysis, and is approximately double that for pregnant women with HIV co-infection⁷. We will compare the rates of perinatal transmission in our study to these historic rates using a one-sided binomial test of proportions and will stratify by HIV status if there is sufficient enrollment of HCV/HIV co-infected participants.

10.5.4 Data and Safety Monitoring Plan

No formal Data and Safety Monitoring Board oversight is planned for this single-arm study; however, the PSRT, as described in section 8.1, will provide oversight. Reviews of adverse events by the PSRT will take place every month. Additionally, Reviews of study progress, including rates of participant accrual, retention, completion of primary and main secondary endpoint assessments, and review of the adverse events will take place approximately every 3 months in person or via a conference call, and as needed. At the time of these reviews, or at any other time, the PSRT may recommend that the study proceed as designed, proceed with design modifications, or be halted/discontinued.

10.5.5 Next Generation Sequencing

On an as needed basis for treatment failures or in the case of perinatal HCV exposures, sequencing of the baseline and post-treatment samples will be carried out using Next Generation Sequencing (NGS) with the Illumina MiSeq platform using a full genome sequencing assay (E1 to NS5B) that works across all 6 major HCV genotypes. Baseline and post-treatment samples will be aligned and compared in HVR1, NS5B and the 5'UTR. If results are equivocal with these 3 regions, additional regions will be compared to allow for determination of relapse versus reinfection. After applying quality control measures to the raw NGS data, the specific haplotypes and their frequencies will be determined using the Global Hepatitis Outbreak and Surveillance Technology (GHOST) platform. Genetic distances between sequences will be calculated and any sequences with a distance of less than the experimentally determined threshold of 0.037 will represent relapse (same virus) and anything at or above this threshold will represent reinfection with a different HCV strain. The

presence of resistance associated substitutions (RAS) in NS3, NS5A and NS5B and their frequency will also be evaluated on pre- and post-treatment samples.

11 DATA HANDLING AND RECORDKEEPING

11.1 Data Management Coordinating Center Responsibilities

Study questionnaires will be developed by data management. The Data Coordinating Center is responsible for maintaining and updating the study questionnaires/RedCap database as needed and for notifying all sites of any updates/changes.

The Data Coordinating Center Statistician or designee will routinely monitor all data entered in the RedCap system. Query reports will be generated and provided to each site on at least a monthly basis. Notification and resolution of queries will be performed according to the coordinating center data management plan. The Protocol Chair will be promptly notified by the Data Coordinating Center statistician of any concerning trends or missing data.

11.2 Source Documents and Access to Source Data/Documents

Each site will maintain source data/documents in accordance with current Good Clinical Practice Guidelines as described by the International Conference on Harmonization (https://www.fda.gov/science-research/clinical-trials-and-human-subject-protection/regulations-good-clinical-practice-and-clinical-trials)/(https://www.canada.ca/en/health-canada/services/drugs-health-products/compliance-enforcement/good-clinical-practices.html)

The study teams will maintain and securely store complete, accurate and current study records. Study records will be maintained on site for the entire period of study implementation.

In accordance with U.S. regulations regarding testing investigational medications, the study investigators will maintain all study documentation for at least two years following the date of marketing approval for the indication of HCV treatment in pregnancy. If no marketing application is filed, or if the application is not approved, the records will be retained for two years after the investigation is discontinued and the U.S. FDA is notified. For research involving children, records shall be retained at least until the pediatric subject reaches the age of 23. For Canadian sites the sponsor shall maintain all records related to the clinical trial for a period of 15 years.

11.3 Quality Control and Quality Assurance

The study sites will conduct quality control and quality assurance procedures in accordance with site SOPs.

12 CLINICAL SITE MONITORING

Up until the time that PPD, Inc. begins monitoring for the multi-site protocol, local monitoring will be performed according to the site's local monitoring plan. The local monitoring plan must be submitted to the Coordinating Center prior to site activation. The local monitoring may be performed by delegates from local/site IND offices or independent monitors. Local plans should include:

- Review local regulatory files, including required essential documents
- Review informed consents for accurate version and completeness
- Verify eligibility
- Perform source document verification to ensure the accuracy and completeness of study data entry, including local laboratory results
- Review and verify accurate and complete documentation and reporting of adverse events.
- Verify proper storage, dispensing, and accountability of investigational study medications.

PPD, Inc. will begin monitoring for all sites once all applicable plans are in place (i.e., contracts, monitoring plans, etc.). Monitoring will be conducted according to the monitoring plan agreed upon by PPD, Inc. and the Protocol Chair. Site monitoring by PPD, Inc. may be conducted in person and/or remotely. All sites must continue to abide by their local institutional policies and procedures and PPD, Inc. will monitor sites per the monitoring plan.

As each local site PI is responsible for submission of their independent IND/CTA to the FDA/Health Canada, all local site requirements for monitoring and FDA/Health Canada regulations in regards to IND/CTA holders are the responsibility of the site PI. Any monitoring and audit reports are to be emailed to the coordinating center regulatory contact upon receipt.

The study investigators also will allow inspection of all study-related documentation by authorized representatives of Gilead Sciences, FDA, Health Canada, IRBs/REBs, PPD, Inc., and applicable Canadian and U.S. regulatory authorities.

13 HUMAN SUBJECTS PROTECTIONS

Study investigators will make efforts to minimize risks to participants. Informed consent will be reviewed in detail with potential participants and all questions will be adequately answered prior to obtaining written informed consent. Informed consent will be obtained prior to performing any study related procedures. All eligibility criteria will be verified prior to initiation of investigational product. Recruitment will begin after the protocol has been submitted to the FDA (as applicable) or Health Canada and after receiving IRB/REB approval and completing requirements of the coordinating center for site activation. The study investigators will permit audits by the Gilead Sciences, the FDA, Health Canada, site IRBs/REBs, and other Canadian and U.S. regulatory authorities or any of their appointed agents.

42

13.1 Institutional Review Boards

The site study staff will ensure that the protocol, informed consent form, and study-related documents (such as participant education and recruitment materials) are reviewed and approved by the respective site IRB/REB prior to starting the study. Any amendments to the protocol or informed consent will be approved by the appropriate IRB/REB prior to implementation.

13.2 Study Coordination

This study is a multi-center study with [name] holding the IND at the University of Pittsburgh and the other sites have received an IND exemption from the FDA, their local IRB/REB, or will obtain a Health Canada CTA. Each site will receive IRB/REB approval from their local IRB/REB. Each study site is responsible for understanding and complying with their local and state research guidelines, regulations and laws.

University of Pittsburgh/UPMC Magee-Womens Hospital will provide coordination for the study.

Close coordination between the study teams is necessary to track recruitment, enrollment, retention, AEs and unanticipated problems in a timely manner and to address other issues that may arise. The PSRT will address issues related to study eligibility, AE management/reporting and unanticipated problems as needed to ensure consistency. Rates of accrual, protocol adherence, retention, and AE incidence will be reported by data management and monitored closely by Data Coordinating Center as well as the PSRT.

